8.8 Biomarkers

CCI

CCI

8.9 Health economics

Health economics parameters are not evaluated in this study.

9 Statistical considerations

Any data analysis carried out independently by the investigator should be submitted to Novartis before publication or presentation.

For each single anti-malarial agent, statistical analyses for Part A and Part B will be performed separately for efficacy and safety outcomes.

For statistical analyses and clinical study reporting, treatment group name, instead of cohort number, will be used for both parts and the pooled analysis. The treatment group will be labeled to include the full dose level of both study drugs for the combination therapy.

For SoC in Part B, pooling across compounds may be considered. Further details will be provided in the statistical analysis plan (SAP).

9.1 Analysis sets

The following analysis sets are considered for the study:

- Randomized analysis set (RAS): all patients who are randomized.
- Full analysis set (FAS): the FAS will be comprised of all patients that have baseline *P. falciparum* count > 0 and take at least one dose of the study treatment during the treatment period. Following the intent-to-treat principle, patients will be analyzed according to the treatment group assigned at randomization.
- The Safety analysis set (SAF) includes all patients who received at least one dose of the study treatment. Patients will be analyzed according to the study treatment received.
- PK analysis set: All patients who have at least one valid (i.e., not flagged for exclusion) PK concentration measurement, receive at least one dose of study drug, and do not have any protocol deviations that impact on PK data.

Full details will be described in the statistical analysis plan (SAP). In general, SAF will be used for safety analysis, RAS for demographics, FAS for efficacy analyses and PK analysis set for all PK analyses, unless otherwise stated.

9.2 Statistical analyses

9.2.1 Participant demographics and other baseline characteristics

Demographic and other baseline data including disease characteristics will be listed and summarized descriptively by single anti-malarial agent, study part, and treatment group for the RAS set.

Categorical data will be presented as frequencies and percentages. For continuous data, mean, standard deviation (SD), median, minimum, and maximum will be presented. For selected parameters, 25th and 75th percentiles will also be presented.

Relevant medical histories and current medical conditions at baseline will be summarized by system organ class and preferred term, by single anti-malarial agent, study part, and treatment group.

9.2.2 Treatments

The SAF will be used for the analyses below. Categorical data will be summarized as frequencies and percentages by part, cohort and treatment group. For continuous data, mean, standard deviation, median, 25th and 75th percentiles, minimum, and maximum will be presented.

The duration of exposure in number of doses to each treatment will be summarized by means of descriptive statistics for the SoC in Part B.

Concomitant medications, rescue and other anti-malarial medications as well as significant non-drug therapies prior to and after the start of the study treatment will be listed and summarized by anti-malarial agent, study part, and treatment group.

9.3 Primary endpoint(s)/estimand(s) analysis

9.3.1 Definition of primary endpoint(s)

The primary efficacy endpoint of the study in Part A is the time to parasite clearance (PCT), as defined as the time (in hours) from the first dose until the first total and continued disappearance of asexual parasite forms which remained at least a further 48 hours. PCT will be calculated based on uncorrected *P. falciparum* asexual parasite counts. The FAS will be used for the analysis.

The primary efficacy endpoint in Part B is the PCR corrected Adequate Clinical and Parasitological Response (ACPR) at Day 29 as defined in [Section 8.3.4](#). The FAS will be used for the analysis.

PCT and PCR corrected ACPR will be used for the primary estimand analyses in Part A and Part B, respectively.

9.3.2 Statistical model, hypothesis, and method of analysis

For Part A, descriptive statistics (mean, standard deviation, median, quartiles) will be provided by treatment group. Individual plots will be provided, and Kaplan-Meier curves will be presented by study part and treatment group. The primary analysis tests whether the upper limit of two-sided 90% CI for the median PCT using Kaplan-Meier estimates for a treatment group is lower than 96 hours.

For Part B, the primary endpoint will be calculated at Day 29 by computing the percent of patients with PCR corrected ACPR for each treatment group. The primary analysis will test for non-inferiority of the combination therapy versus SoC based on the dual efficacy criteria as specified below, **CCI**

Informative priors for the SoC will be used, while for the combination treatment prior information may be vague or informative depending on whether relevant prior information is available.

[Table 9-1](#) shows the historical data about the 28-day cure rate observed in historical trials for the SoC.

CCI

Further details on the prior used for the combination therapy will be specified in the Cohort Specific Information in [Section 12](#) and details of the statistical methodology will be outlined in the SAP.

The dual efficacy criteria are the following:

CCI

9.3.3 Handling of intercurrent events of primary estimand

The primary analysis in Part A will account for below mentioned inter-current events using a hypothetical strategy. If a patient receives any rescue anti-malarial medication or receives other concomitant medication having an effect on malaria for any reasons, the time-to-event PCT will be set to Day 7 from the day of the occurrence of the event.

The primary analysis in Part B will account for the below mentioned inter-current events using a principal stratum strategy. Data will be handled as follows:

9.3.4 Handling of missing values not related to intercurrent event

For handling missing values in the primary analysis in Part A, the following strategies will apply:

- If the parasite is not cleared and the last parasite count is missing but not related to intercurrent event, the time-to-event PCT will be censored at Day 7.
- If an intermediate parasite count is missing between 2 existing measures (e.g., such as missing sample, technical reason, etc.):
 - If both previous and following measures are quantifiable and above the limit of quantification, the intermediate value will be considered as presence of parasite.
 - If both previous and following measures are below the limit of quantification, the missing value will be considered as no presence of parasite.
 - If the previous measure is quantifiable and above the limit of quantification, but not the following measure, the intermediate value will be considered as presence of parasite.

In Part B no imputation of data will be performed.

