### 2.5.2 Statistical hypothesis, model, and method of analysis

For Part A, PCT descriptive statistics (mean, standard deviation, median, quartiles) will be provided and Kaplan-Meier curves will be presented. The median PCT and corresponding 2-sided 90% CI will be reported.

For Parts B & C, the primary endpoint will be calculated at Day 29 by computing the percent of patients with PCR-corrected ACPR at Day 29 where presence of *P. falciparum* asexual forms on Day 8 or later is considered as failure (not ACPR) only if the parasite strain observed was already present at baseline based on PCR genotyping. Refer to [Section 2.1.2](#) and [Section 2.1.2.1](#) for details. Note: the primary endpoint is binary with 2 outcomes (ACPR or not ACPR). Beside recrudescence, a patient’s outcome can be classified as not ACPR due to reasons such as missing PCR genotyping at baseline (i.e. PCR result is undetermined), etc. ([Section 2.5.3](#)).

The primary analysis will test for non-inferiority of the CCI based on the dual efficacy criteria as specified below, using a Bayesian approach. CCI

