### 2.5.3 Handling of intercurrent events

The primary analysis in Part A will account for the below mentioned intercurrent events using a hypothetical strategy. If a patient receives any rescue anti-malarial medication or receives other concomitant medication with anti-malarial activity for any reasons within the first 7 days and before the parasites are cleared, time-to-event PCT will be set to Day 7 (144 hours).

The primary analysis in Parts B & C will account for the below mentioned intercurrent events using a principal stratum strategy. Data will be handled as follows:

[figure not shown]
CCI

The number and percent of patients with intercurrent events will be provided for each intercurrent event using FAS.

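### Censoring an uncleared patient at Day 7 instead of at the last parasite count biases the Part A median PCT upward and costs power; separately, the rescue rule is composite in kind but labelled hypothetical

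*Protocol*

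**What the plan says.** - **Endpoint (Protocol 9.3.1).** PCT runs from first dose to the "first total and continued disappearance of asexual parasite forms which remained at least a further 48 hours".
- **Criterion (Protocol 9.3.2).** Part A asks whether the "upper limit of two-sided 90% CI for the median PCT using Kaplan-Meier estimates for a treatment group is lower than 96 hours". SAP 2.5.2, where readable, states only that "The median PCT and corresponding 2-sided 90% CI will be reported". Both documents also plan a mean and SD of PCT.
- **Missing last count (Protocol 9.3.4).** For a patient who has not cleared, where "the last parasite count is missing but not related to intercurrent event, the time-to-event PCT will be censored at Day 7". The corresponding Part A text in SAP 2.5.4 is blacked out.
- **Rescue or other anti-malarial medication.** Protocol 9.3.3: "the time-to-event PCT will be set to Day 7 from the day of the occurrence of the event". SAP 2.5.3: "time-to-event PCT will be set to Day 7 (144 hours", and only if the medication is given in the first 7 days and before clearance. Both sections call the strategy hypothetical. Neither says whether the assigned value is an event or a censored time.
- **Safeguards.** The sensitivity sections (Protocol 9.3.5, SAP 2.5.5) address only Part B, or Parts B and C. Protocol 9.3.6 and SAP 2.5.6 plan no supplementary analysis for Part A.

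**The concern.** A patient last seen uncleared at 30 h and then lost stays in the Kaplan-Meier risk set until 144 h as if every later film had been positive. The rule covers losses that the plan itself regards as unrelated to intercurrent events, and for such losses the usual censoring time is the last count. Protocol 8.3.5 does this for recrudescence and reinfection, where follow-up ends at the last parasite assessment. No reason for treating PCT differently is visible.

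At stake are the reported median, the primary criterion for each Part A dose group, and the comparability of dose groups with unequal losses. Part A efficacy data feed the Part B dose decision (Protocol 3.1).

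The rescue rule raises a different issue. A hypothetical strategy targets the clearance time that would have occurred without rescue. Assigning the last time on the scale instead treats rescue as an unfavourable outcome, which is a composite strategy. SAP 1.2.3 uses that name when non-study anti-malarials count against uncorrected ACPR.

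**Working it through.** **1. The plan's own figure.** Day 1 is the day of first dose, so Day 7 is (7 − 1) × 24 = 144 h. This reproduces the SAP's 144 hours.

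**2. Direction.** If nobody leaves the risk set before 144 h, the Kaplan-Meier estimate at any earlier time is the fraction not yet recorded as cleared. Moving a lost patient from the true clearance time to 144 h can only raise that fraction. The median and its upper limit therefore cannot fall below their complete-data values.

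**3. Example by hand (invented data).** Twenty patients clear at 30, 34, …, 106 h. The three who would clear at 46, 66 and 86 h are lost at 24 h. The median is the first time with S ≤ 0.5. The upper 90% limit is the first time at which S^exp(−1.645 × √g / |ln S|) ≤ 0.5, where g = (1 − S)/(nS) and n is the number still at risk after 24 h.

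- Limit with n = 20: at S = 7/20 the bound is 0.521; at S = 6/20 it is 0.470. The limit is the 14th clearance.
- Limit with n = 17: at S = 6/17 the bound is 0.538; at S = 5/17 it is 0.478. The limit is the 12th clearance.

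| Handling | Median | Upper 90% limit |
|---|---|---|
| Complete data (n = 20) | 10th clearance, 66 h | 14th, 82 h |
| Censored at 144 h, as written (n = 20) | 10th observed, 74 h | 14th observed, 94 h |
| Event at 144 h (n = 20) | 74 h | 94 h |
| Censored at last count, 24 h (n = 17) | 9th observed, 70 h | 12th observed, 82 h |

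Simple mean with complete data: 68.0 h, a total of 1,360 h. With 144 h filled in: (1,360 − 198 + 432)/20 = 79.7 h, where 198 = 46 + 66 + 86 and 432 = 3 × 144.

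**4. Chance of meeting the 96 h criterion, by simulation.** Arm size and sampling times are blacked out, so these are assumptions: 20 patients, log-normal PCT with log-SD 0.35, continuous clearance times, true median 66 h unless stated, log-log 90% limits. Percentages are patients selected for loss, who count as lost only if still uncleared at that time.

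| Setting | Censored at last count | As written |
|---|---|---|
| 10% lost at 24-48 h | 0.97 | 0.87 |
| 20% lost at 24-48 h | 0.96 | 0.60 |
| 10% or 20% lost at 72-144 h | 0.98 | 0.98 |
| True median 48 h, 10% lost at 24-48 h | 1.00 | 0.99 |

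**5. Range under other assumptions.**
- PCT rounded up to a 12-hour sampling grid, losses at 24-48 h: 0.77 versus 0.54 at 10%, and 0.72 versus 0.25 at 20%. With losses at 72-144 h and 10% lost: 0.79 under both.
- 30 patients, log-SD 0.5, true median 72 h, losses at 0-72 h: 0.81 versus 0.58 at 10%, and 0.75 versus 0.33 at 20%.
- 15 patients, log-SD 0.5, true median 48 h, losses at 0-72 h: 0.99 versus 0.95 at 10%, and 0.98 versus 0.82 at 20%.
- True median 24 h, 15 or 30 patients: at least 0.996 under either rule.

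**6. False passes.** With log-SD 0.5, 15 or 30 patients and a true median of exactly 96 h, the criterion is met in 0.004-0.035 of arms under the written loss and rescue rules. With censoring at the last count, or at rescue, it is met in 0.057-0.069; with complete data, in 0.045-0.065. The nominal rate is 0.05.

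**7. Event or censored at 144 h.** The two codings gave the same median and upper limit in every simulated dataset where both lay below 144 h. They differ only in the tail of the curve.

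**The case against.** **The size depends on early loss.** Patients stay at the site for at least 3 days (Protocol 3.1), so losses at 24-48 h should be uncommon, and later losses make almost no difference. This stands and limits the point. The missing-count wording could also mean only the final scheduled count, in which case Day 7 and the last observed count nearly coincide. But no other visible rule covers a patient lost at 30 h, so the text still needs correcting.

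**The quoted rule may not be current.** The protocol supplied is Amendment 2 of June 2023. The SAP follows protocol version 03 of 20 March 2024, its Part A missing-value text and its list of changes are blacked out, and its readable text does not repeat the 96 h test. This stands as a reason to confirm, not to assume a mismatch.

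**The strategy label may be explained elsewhere.** The primary estimand text is blacked out. The handling that can be read nevertheless does not estimate an outcome without rescue.

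**Stronger readings to avoid.** A reader might infer that rescued patients are counted as having cleared at 144 h. The documents say only that the time is set there, and the choice does not affect a median or limit below 144 h. A reader might also infer a distorted comparison in Parts B and C. SAP 2.6.4 does reuse the Part A missing-value strategy for PCT, but that strategy's text in SAP 2.5.4 is blacked out, and SAP section 3 plans no formal PCT comparison there.

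**Conclusion.** The concern holds in a limited form. Protocol 9.3.4 counts unobserved time as observed non-clearance and biases the median PCT and its upper limit upward. The harm is lost power and an overstated median, not a spurious success. At 20 patients and a true median of 66 h, the loss in the chance of passing is about 0.10 (0.97 − 0.87) with 10% lost early, and 0.36 (0.96 − 0.60) with 20%. It is negligible for losses after the inpatient stay, and small at a true median of 48 h with 10% lost. These sizes rest on the assumed arm size, spread, sampling and timing of loss; the direction does not.

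The rescue rule's label and handling do not match, and its coding is unspecified. That is a matter of clarity for the 96 h criterion, but a substantive one for a simple mean and SD if 144 h is filled in.

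**What to change.** - Censor losses unrelated to intercurrent events at the last available parasite count. Keep the Day 7 rule as a conservative sensitivity analysis for Part A.
- Code rescued patients as not cleared by Day 7, that is, censored at 144 h, and call the strategy composite. Do not censor at the time of rescue: rescue probably marks slow clearers, so such censoring would be informative and could favour the drug.
- Do not compute a simple mean and SD over assigned 144 h values. The planned median, quartiles and Kaplan-Meier curves suffice, or use a restricted mean to 144 h.
- Reconcile Protocol 9.3.3 with SAP 2.5.3 on which rescue events trigger the rule. Read literally, the protocol sentence could reset PCT in a patient who had already cleared, and Protocol 6.8.3 has an anti-malarial given on Day 29 in Part A. The SAP's restriction avoids this.
- Confirm that the blacked-out SAP 2.5.4 rule agrees with the protocol.

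The cost is a few lines of wording and a short change to the PCT derivation, with no new data. The downside is a slightly less conservative primary analysis if some losses are in fact failures, which the retained sensitivity analysis would show.

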9.3.5 Sensitivity analyses

In Part B, 2-sided 80% confidence intervals for the difference to SoC will be constructed using the Wilson uncorrected method.

9.3.6 Supplementary analysis

Supplementary analyses are not planned for Part A. For Part B, the computation of percent of patients with PCR uncorrected ACPR (using the FAS) and 95% confidence intervals for each treatment group will be computed, such as described in [Section 9.3.2](#). PCR-corrected ACPR rate and PCR-uncorrected ACPR rate will be also calculated and plotted using the Kaplan-Meier method for each single anti-malarial agent, study part and treatment group in the FAS.

9.4 Secondary endpoint(s)/estimand(s) analysis

The secondary efficacy variable in Part A is the PCR corrected ACPR, at Day 29 as defined previously in [Section 9.3.1](#).

The secondary efficacy variable in Part B is the PCT as defined previously in [Section 9.3.1](#).

The secondary estimand will be used to analyze the PCR corrected ACPR in Part A and PCT in Part B.

In addition, pharmacokinetics and safety and tolerability will also be assessed.

9.4.1 Efficacy and/or Pharmacodynamic endpoint(s)

The secondary analysis for Part A will be the computation of percent of patients with PCR corrected (using the RAS) and uncorrected ACPR (using the FAS) and 95% confidence intervals for each treatment group as described in [Section 9.3.2](#). No hypothesis testing will be performed. CCI

At each visit, the percent of patients with PCR corrected and uncorrected ACPR and 95% confidence intervals will be provided using Clopper-Pearson method for each single anti-malarial agent and for each treatment group. 2-sided 80% confidence intervals for the difference to SoC at each visit will be constructed using the Wilson uncorrected method. At each visit, PCR uncorrected failure will be classified into, ETF before Day 4, LCF before Day 8, recrudescence, new infection, negative PCR, missing PCR, or missing assessment. The classification will be tabulated using the FAS.

CCI

If relevant, key efficacy endpoints will be summarized by treatment group for subgroups of participants with or without relevant resistance mutations.

9.4.2 Safety endpoints

For all safety analyses, the SAF will be used. All listings and tables will be presented by single anti-malarial agent, study part, and treatment group.

Safety summaries (tables, figures) include all post treatment data with the exception of baseline data which will also be summarized where appropriate (e.g., change from baseline summaries). In particular, summary tables for adverse events (AEs) will summarize using all post-treatment events, with a start date on or after the first treatment (treatment-emergent AEs).

Adverse events

All information obtained on adverse events will be displayed by each single anti-malarial agent, study part, treatment group and patient.

The number (and percentage) of patients with treatment emergent adverse events (events started after the first dose of study medication or events present prior to start of treatment but increased in severity based on preferred term) will be summarized in the following ways:

- by each single anti-malarial agent, study part, treatment group, primary system organ class and preferred term.
- by each single anti-malarial agent, study part, treatment group, primary system organ class, preferred term and maximum severity.
- by each single anti-malarial agent, study part, treatment group, Standardized MedDRA Query (SMQ) and preferred term.

Separate summaries will be provided for study medication related adverse events, death, serious adverse events, other significant adverse events leading to discontinuation, and adverse events leading to dose interruption in the SoC of Part B.

A patient with multiple adverse events within a primary system organ class is only counted once towards the total of the primary system organ class.

Vital signs

All vital signs data will be listed by single anti-malarial agent, study part, treatment group, patient, and visit/time and if ranges are available, abnormalities (and relevant orthostatic changes) will be flagged. Summary statistics will be provided by single anti-malarial agent, study part, treatment group, and visit/time.

12-lead ECG

PR, QRS, QT, QTcF, and RR intervals will be obtained from 12-lead ECGs for each patient during the study. ECG data will be read and interpreted (centrally).

Categorical Analysis of QT/QTc interval data based on the number of patients meeting or exceeding predefined limits in terms of absolute QT/QTc intervals or changes from baseline will be presented. In addition, a listing of these patients will be produced (by each single anti-malarial agent, study part and treatment group).

All ECG data will be listed by each single anti-malarial agent, study part, treatment group, patient and visit/time, abnormalities will be flagged. Summary statistics will be provided by each single anti-malarial agent, study part, treatment group, and visit/time.

Clinical laboratory evaluations

All laboratory data will be listed by each single anti-malarial agent, study part, treatment group, patient, and visit/time and if normal ranges are available abnormalities will be flagged. Summary statistics will be provided by each single anti-malarial agent, study part, treatment group, and visit/time. Shift tables for each single anti-malarial agent and study part using the low/normal/high classification will be used to compare baseline to the worst post-treatment value.

9.4.3 Pharmacokinetics

The PK analysis set will be used for the pharmacokinetics analyses.

CCI

Table 9-2 Non-compartmental pharmacokinetic parameters

AUClast	The AUC from time zero to the last measurable concentration sampling time (tlast) (mass x time x volume ⁻¹)
AUCinf	The AUC from time zero to infinity (mass x time x volume ⁻¹)
Cmax	The maximum (peak) observed plasma, blood, serum, or other body fluid drug concentration after single dose administration (mass x volume ⁻¹)
Tmax	The time to reach maximum (peak) plasma, blood, serum, or other body fluid drug concentration after single dose administration (time)
Lambda_z	Smallest (slowest) disposition (hybrid) rate constant (time ⁻¹) may also be used for terminal elimination rate constant (time ⁻¹)
T1/2	The elimination half-life associated with the terminal slope (λ_z) of a semi logarithmic concentration-time curve (time). Use qualifier for other half-lives
CL/F	The total body clearance of drug from the plasma (volume x time ⁻¹)
Vz/F	The apparent volume of distribution during terminal phase (associated with λ_z) (volume)

CCI

